1. Sustained Remission (“Recovery”) Rate. At the end of the 24 week post treatment follow-up, patients who received rTMS who remitted will be more likely to continue in remission, i.e. show “recovery,” than patients who received sham rTMS who remitted.

2. Response Rate. Active rTMS will result in a greater response rate ($\geq 50\%$ decrease in HRSD24) than sham rTMS after treatment.
3. Secondary consequences of TRMD will improve with rTMS treatment, i.e. quality of life, symptoms of PTSD and substance abuse will improve with rTMS treatment.
4. Moderators of Response. Age, severity of symptoms at baseline, type of comorbidity (PTSD, substance abuse, or both), duration of illness and prior treatment resistance may affect or “moderate” treatment response.
5. Cost Offset. TRMD patients who received active rTMS will have lower average VA costs of care following treatment than will TRMD patients who did not receive rTMS.

Secondary Objectives:

1. To evaluate the durability of benefit of rTMS in treatment of TRMD (patients receiving rTMS are more likely to remain in remission at 24 weeks post treatment than those receiving sham). This reflects the ACNP criteria for “recovery” (Rush et al., 2006) that requires “recovery” to be defined by at least 3 months of “remission”.
2. To evaluate the efficacy of rTMS in bringing about a significant decrease in depressive symptoms ($\geq 50\%$ decrease in the Hamilton Rating Scale for Depression). This is consistent with the ACNP criteria for “response” (Rush et al., 2006).
3. To determine whether depressive symptoms, suicidality, PTSD symptoms, substance abuse, cognitive function and quality of life improve with rTMS treatment.
4. To determine whether age, severity of symptoms at baseline, type of comorbidity, duration of illness, and prior treatment resistance, affect or “moderate” response to rTMS.
5. To evaluate the cost offset of rTMS in the treatment of depression in the VA Healthcare System.

Design and Methods:

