COMORBIDITIES	INCLUDED	EXCLUDED		EXCLUDED
SUICIDALITY	ASSESSED	NOT ASSESSED		NOT ASSESSED
HEALTH ECONOMICS	ASSESSED	NOT ASSESSED		NOT ASSESSED
AMOUNT OF TREATMENT	20-30 SESSIONS	15-30 SESSIONS		20 SESSIONS
PRIMARY ASSESSMENT FOR REMISSION	AT END OF TREATMENT PHASE	AT END OF TREATMENT PHASE		AFTER 4 WEEKS OF TREATMENT

II. STUDY OBJECTIVES

A. Primary Objective

To assess the efficacy of rTMS in veterans to bring about remission of TRMD.

B. Secondary Objectives

1. To evaluate the durability of benefit of rTMS in treatment of TRMD (patients receiving rTMS are more likely to remain in remission at 24 weeks post treatment than those receiving sham).

2. To evaluate the efficacy of rTMS in bringing about a significant decrease in depressive symptoms (a $\geq 50\%$ decrease in the Hamilton Rating Scale for Depression).
3. To determine whether depressive symptoms, suicidality, PTSD, substance abuse, cognitive function and quality of life improve with rTMS treatment.
4. To determine whether age, severity of symptoms at baseline, comorbidity with substance abuse or PTSD, duration of illness, and prior treatment resistance, predict differential treatment response.
5. To evaluate the cost effectiveness of rTMS in the treatment of depression in the VA Healthcare System.

III. OUTCOME MEASURES

A. Primary Outcome Measures

The proportion of participants achieving remission from depression based on the Hamilton Rating Scale for Depression of ≤ 10 at the end of the acute treatment phase.

B. Secondary Outcome Measures

The selection of secondary outcome measures is based on their use in previous studies in major depression, where appropriate.

1. Depression measured by Montgomery-Asberg Depression Rating Scales (MADRS)
2. Suicide Ideation measured by Beck Scale for Suicide Ideation (BSS)
3. Depression measured by Beck Depression Inventory (BDI)
4. Quality of Life measured by the VR-36
5. Cognitive Function as measured by a neuropsychological battery

IV. STUDY DESIGN

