All data collected for this study will be handled and used in compliance with both the CSP and the Perry Point CSPCC data security plans. All patient level data will be treated as protected health information. Data will be transmitted from participating sites using secure servers. Study personnel at CSPCC, CRPCC, and at participating sites will be required to complete annual training courses. These courses will cover good clinical practices, human subjects' protection, cyber security, and privacy policy. Any data security breaches will be immediately reported. Access to patient level data at CSPCC or CRPCC, will be obtained through user accounts which will be protected by strong passwords. File protections will be used to limit access to members of the study group. Patient level data will never be stored on portable storage devices unless it is encrypted, explicitly authorized, and use specific.

VIII. BIOSTATISTICAL CONSIDERATIONS

A. Sample Size

The primary hypothesis of the study is that in VA patients with TRMD, rTMS will result in a greater remission rate at the end of acute treatment than sham rTMS. The primary outcome measure in this study is success or failure to achieve remission from depression as defined by a score on the Hamilton Rating Scale for Depression (HRSD24) of 10 or less. The primary analysis will be done as an “intent-to-treat” analysis, i.e. patients will be analyzed in the groups to which they were randomized and drop-outs will be considered treatment failures. The primary hypothesis will be addressed using a logistic regression model with PTSD diagnosis, history of substance abuse, and site as covariates.

Based on review of the studies reported in the Introduction Section, the Planning Committee felt that a 10% difference between treatments would be of clinical relevance given the severity of the illness. With a sample size of 180 per group, the proposed study will have a power of 81% to detect an absolute difference between groups of 10% in the percentage of those participants who remit (6% sham and 16% rTMS). Thus, a total of 360 patients will be randomized. This goal of 360 patients, larger than any previous study, also provides a measure of protection should some assumptions be wrong.

B. Analysis Plan

1. Site Effects and Baseline Comparability

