Some secondary outcome measures, such as sustained response rate (“recovery”) and response on secondary outcome measures, can also be analyzed using logistic regression models. Other potential secondary analyses include continuous variables such as: change in suicidality, change in cognitive function and change in quality of life (QOL). The effect of rTMS on such continuous measures will be determined using random regression and similar techniques that maximize the use of available data in repeated measures designs.

Potential moderators of treatment response also will be analyzed using multivariate analysis of variance or regression techniques. In addition, exploratory analyses will be performed using signal detection techniques (Receiver Operator Characteristics or ROC) to attempt to identify novel moderators predictors of response. The following gives examples of some potential

analyses that may be carried out that use random regression techniques, which may be more sensitive to change than the logistic regression analyses.

a. Random regression approach to efficacy analyses

Random regression models will be used to test and evaluate treatment efficacy (see e.g., Gibbons et al., 1993). Such models trace the individual trajectories over time and, in effect, use available information to impute any missing data for comparable subjects. They thus compare the groups on a parameter describing the trajectory (e.g., the subject's response rate over time). This method not only minimizes loss of power and bias due to dropouts (for analytical purposes there are none), but also amplifies the reliability of measures using repeated measures per subject and thus usually increases power.

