modified or terminated. The DMC can consider patient safety or other circumstances as grounds for early termination, including either compelling internal or external evidence of treatment differences or infeasibility of addressing the study hypotheses (e.g., poor patient intake, poor adherence to the protocol). The DMC will meet annually to review data reports prepared by the CSPCC. At the six-month interval between the annual meetings, the DMC will receive a data report for their review. Any member of the DMC can ask for a meeting of the group if he/she feels that it is necessary, based upon the data. This group will receive outcome data during the course of the study.

In order for the DMC to make its recommendation for continuation of the study, it will be necessary for them to see the analyses for the primary outcome measure every time that the report is run and it is possible to calculate the primary outcome measure. Periodic monitoring of interim results can significantly affect the probability of making an incorrect decision. A number of formal techniques have been developed for interpreting interim results. At the organizational meeting, the DMC will select the technique that it wants to use to monitor the study. Suggested techniques are the Haybittle-Peto and Lan-DeMets group sequential boundaries. For the Haybittle-Peto method, a constant z-statistic is used as the monitoring boundary. The Lan-DeMets procedure produces decision boundaries that are quite conservative over the first several looks and then gradually converges to the nominal alpha levels as the final look is approached. Figure 3 gives an example of the Lan-DeMets boundaries for five looks at an alpha level of 0.05.

Figure 3. Lan De - Mets Group Sequential Monitoring Boundaries

4. Human Rights Committee (HRC)

The Human Rights Committee (HRC) will conduct annual site visits to ensure that patients' rights and safety are being properly protected.

5. Internal Reviews

The Study Chairman, the Study Biostatistician, the CRP and the CSPCC Project Manager will communicate regularly and frequently to review study status. Discussion items will include overall and site-specific enrollment, regulatory issues, protocol compliance and data completeness and quality. Action plans to deal with identified problems will be developed.

6. Site Monitoring, Auditing and Resource Team (SMART)

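### Secondary hypothesis 1 compares durability only among patients who remitted (about 29 against 11), which is neither a randomised nor an informative comparison, and the analysis section names the endpoint differently

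*Protocol*

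**What the plan says.** **Hypothesis.** In the Executive Summary, Secondary Hypotheses item 1 is headed as sustained remission, glossed as recovery. It says that "patients who received rTMS who remitted will be more likely to continue in remission" at 24 weeks after treatment "than patients who received sham rTMS who remitted". Both sides of the comparison are restricted to remitters.

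**Objective.** Secondary Objective 1, in the Executive Summary and again in Section II.B, is worded by arm: "patients receiving rTMS are more likely to remain in remission at 24 weeks post treatment than those receiving sham". The Executive Summary version adds that recovery requires at least three months of remission.

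**Analysis.** Section VIII.C begins its treatment of this endpoint with "Some secondary outcome measures, such as sustained response rate", glosses that as recovery, and proposes logistic regression. It gives no threshold, visit rule or denominator. Response and remission are separate criteria in this protocol: a fall of at least 50% in HRSD24 (hypothesis 2), and an HRSD24 of 10 or less (Section VIII.B.2).

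**Planning rates.** Section VIII.A assumes "6% sham and 16% rTMS" with 180 per arm.

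**The concern.** Remission at the end of acute treatment is the primary outcome. Randomisation makes the arms comparable at baseline, but not the subsets that later remit. If rTMS brings some harder-to-treat patients into remission, the sham remitters are the smaller and possibly better-prognosis group. A difference in later relapse, or its absence, could then reflect who remitted and not what the treatment did.

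The comparison also rests on few patients, because few are expected to remit, especially on sham. A null result would be uninterpretable and a positive one would not be a randomised result. Durability is part of the trial's stated purpose and is its first secondary hypothesis.

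The naming conflict adds to this. With the criterion and the denominator both open, the endpoint could be settled after the data are seen.

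**Working it through.** **1. The plan's own figure.** Section VIII.A says the study "will have a power of 81% to detect an absolute difference between groups of 10" percentage points. Alpha and sidedness are not stated there; two-sided 0.05 is assumed (0.05 appears only in the monitoring example in Section X.B.3). With 180 per arm, 6% and 16%, the pooled rate is 0.11:

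- SE under the null: √(2 × 0.11 × 0.89 / 180) = 0.0330
- SE under the alternative: √((0.06 × 0.94 + 0.16 × 0.84) / 180) = 0.0326
- Uncorrected power: Φ((0.10 − 1.96 × 0.0330) / 0.0326) = 86.1%
- With continuity correction (1/180 subtracted from the difference): 82.0%

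The stated 81% agrees with the corrected formula to within rounding, so the primary sample size is not in question.

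**2. Expected remitters.** 180 × 0.16 = 28.8 on rTMS and 180 × 0.06 = 10.8 on sham, or about 29 and 11. The central 95% binomial ranges are 20–39 and 5–17.

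**3. Precision among remitters.** The widest half-width (both proportions at 0.5) is 1.96 × √(0.25/29 + 0.25/11) = 0.347, about 35 points.

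**4. Power among remitters.** The protocol gives no durability rates, so these are assumptions. Power is by exact enumeration for 29 v 11, two-sided 0.05:

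| rTMS v sham, sustained | Fisher | Chi-square |
|---|---|---|
| 70% v 50% | 17% | 23% |
| 70% v 40% | 35% | 43% |

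By the normal approximation, the difference detectable with 80% power is about 41 to 47 points for sham durability of 20% to 50%.

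**5. All randomised as denominator, equal durability.** Sustained remission is the remission rate times durability. With the same durability in both arms (assumed):

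| Durability | Sham v rTMS, of 180 each | Fisher power |
|---|---|---|
| 40% | 2.4% v 6.4% | 36% |
| 50% | 3.0% v 8.0% | 47% |
| 60% | 3.6% v 9.6% | 56% |
| 70% | 4.2% v 11.2% | 65% |

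In these settings the remitters-only test rejects about 3% (Fisher) to 5% (chi-square) of the time, although more than twice as many rTMS patients are durably well.

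**6. Direction of selection, illustration only.** A latent prognosis is allowed to drive both remission and durability, treatment affects remission (6% to 16%) but not durability, and base durability is 30% to 50%. Sham remitters then look more durable by about 2 points at a loading of 0.3, 4–5 at 0.5 and 7–10 at 0.7. Nothing in the protocol supports a particular loading.

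**7. The two names.** Eligibility requires an HRSD24 of at least 20. At a baseline of 20, response and remission both mean a score of 10 or less. At a baseline of 40, a score of 20 is response but not remission. Sustained response and sustained remission can therefore classify the same patient differently.

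**The case against.** The best defence is that durability given remission is a legitimate clinical question, and that equal durability in both arms is the correct answer to it when rTMS only adds remitters; the primary analysis already counts those. This stands as far as the question goes. It does not make the remitter subsets comparable or larger.

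Arm-level follow-up comparisons also exist: all patients enter the 24-week follow-up (Section VI.E), the longer-term random regression in Section VIII.C is not restricted to remitters, and Section VIII.F compares sustained remission across the two arms. These soften the consequences but leave hypothesis 1 as written.

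A reader might infer more than the protocol supports:

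- *That the objective contradicts the hypothesis.* Remaining in remission can presuppose having remitted. The objective is ambiguous about the denominator, no more.
- *That the three-month criterion conflicts with the hypothesis.* A patient in remission throughout 24 weeks meets it.
- *That Section VIII.C defines a different endpoint.* It names one differently, in a single phrase among examples.
- *That the all-randomised analysis is simply more powerful.* With 70% v 40% durability it gives 11.2% v 2.4% and Fisher power of 91%, against 35% among remitters. The two tests have different null hypotheses, and much of the 91% comes from the primary remission effect, as step 5 shows. The contrast is not like for like.
- *That a material bias against rTMS has been shown.* The illustration gives a direction under one model. Its size depends on the loading and is small beside a 35-point half-width.

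**Conclusion.** The point holds. Hypothesis 1 conditions both arms on the post-randomisation primary outcome and, at the protocol's own rates, leaves about 29 v 11 patients. The counts are planning expectations that follow directly from Section VIII.A; the power figures rest on assumed durability rates and an assumed two-sided 0.05. Separately, Section VIII.C's name for recovery conflicts with the hypothesis and with Section VIII.F.

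This should be corrected, but it does not threaten the trial. It concerns a secondary hypothesis with no power claim. The primary endpoint, sample size, safety monitoring and conduct are unaffected, and the data for a sound analysis are already collected.

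**What to change.** - Make the main, confirmatory analysis of hypothesis 1 the proportion of **all randomised** participants with sustained remission: HRSD24 of 10 or less at the end of acute treatment and maintained to week 24 under one visit rule stated in advance. The monthly visits covering the last three months are one reasonable choice.
- Count non-remitters and dropouts as not sustained, as the primary analysis counts dropouts as failures, and use the primary logistic model (PTSD, history of substance abuse and site as covariates).
- Keep the remitters-only comparison as descriptive, with its confidence interval.
- Word Objective 1 so that the denominator is explicit, and in Section VIII.C replace the reference to sustained response with sustained remission rate.

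The cost is wording only. Table 2 already schedules the HRSD at follow-up weeks 4 to 24, and non-remitters are followed too, so no patients or visits are added. One limitation should be stated with the new endpoint: it combines initial remission with durability. It answers whether more rTMS patients are durably well and does not isolate durability given remission.

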***B= Baseline**

***S= Screening**

¹ Sessions 21-25 and 26-30 may not be required if patient goes into remission earlier

² Must be conducted within 7 days prior to randomization

³ Termination Form will be completed at the end of the study OR when a patient decides to end study participation prior to the study completion date; i.e., a patient decides to withdraw or leave the study for any reason, withdraws consent, or is suspended from the study.

1. Demographics, Medical History, Physical Exam, Laboratory, Toxicology, Pregnancy

Test and Medication Use. Relevant demographics will be collected as to age, gender, racial/ethnic grouping, military history and income. In addition, a standard Medical History and Physical Exam will be completed as well as laboratory tests including a Complete Blood Count (CBC), electrolytes (chemistry), thyroid panel and a liver function test. An alcohol test and urine drug toxicology screen will be conducted prior to randomization and also randomly during the following time points of study participation:

- Acute Treatment Phase: 2nd, 4th, and 6th (if still in acute treatment) weeks
- Taper Phase: 2nd week
- Follow-up Phase: 1st, 3rd, and 5th months

A pregnancy test will be conducted on all female patients of childbearing potential (that is, all women except for those who are post menopause for > 2 years or who have a history of hysterectomy or surgical sterilization) prior to randomization and every four weeks during the study. Information on medication use (prescription, natural food products, and “over the counter”) will be collected at screening and updated after each block of five sessions during the treatment phase and every four weeks during the follow-up phase.

2. Structured Clinical Interview for DSM-IV (SCID) (First et al., 2002). The Structured Clinical Interview for DSM-IV Axis I Disorders (SCID) is a semi-structured interview that is used to make the major DSM-IV Axis I diagnoses in the most uniform manner possible.

3. Antidepressant Treatment History Form (ATHF) (Sackeim et al., 1990). The ATHF provides a uniform and rigorous method of eliciting and recording a patient’s past experience using antidepressant medications. The ATHF provides detailed information about which treatments the patient has received during the index episode and over his/her lifetime. Specific criteria are used to evaluate the adequacy (e.g., dose and duration) of each treatment trial, and a determination is made, for each trial, whether the patient manifested treatment resistance (did not satisfactorily respond at adequate dose and duration) or whether the stringent dose and duration requirements could not be met (treatment intolerance).

Measures of Substance Abuse and Post-traumatic Stress

To perform moderator analyses determining if these comorbid conditions are associated with differential response to treatment, relevant measures will be collected. Since all subjects, at the time of the protocol, will not be abusing substances, the most relevant measures will be history of duration and severity of substance abuse, in particular alcohol abuse. Additional measures will quantify relevant aspects of PTSD.

4. Lifetime Drinking History (Skinner & Sheu, 1982). Lifetime alcohol consumption will be assessed using the Lifetime Drinking History (LDH) instrument as designed by Skinner and Sheu (1982) and refined by Sobell and colleagues (1988, 1990). LDH is the state-of-the-art validated assessment instrument for obtaining quantitative data on the frequency, amount, duration, and pattern of lifetime alcohol consumption beginning from the onset of regular drinking. Aggregate indices for total lifetime drinking can be assessed with moderate to high reliability (Skinner & Sheu, 1982; Sobell et al., 1990, 1988). It is recognized that the pattern of

drinking behavior (i.e. chronic regular drinking vs. binge drinking) may affect outcome measures. Therefore, drinking assessment will include measures of total alcohol consumption, typical and maximum alcohol consumption per occasion, average daily and average monthly intake (measures of drinking intensity reflecting both frequency of drinking occasions and dose per occasion), both for the last six months (current drinking) and for lifetime (lifetime drinking history).

5. Michigan Alcohol Screening Test (MAST). The MAST is self-report measure for the detection of alcoholism. It consists of 25 yes-no questions that are differentially weighted depending on the severity of the symptom addressed in each item. The score ranges for interpretation of the MAST are as follows: 0-4 = absence of alcoholism; 5-6 = possible alcoholism; 7 and up = probable alcoholism. The measure will be used to assess alcohol abuse at baseline and then at the end of acute treatment (intervention) and the follow-up phase.

6. Drug Abuse Screening Test (DAST) (Skinner, 1982). The DAST is a self-report measure for the detection of drug abuse or dependence on a range of psychoactive substances, other than alcohol. The DAST was adapted from the MAST and shares a similar item structure. A score of 5 or higher is indicative of a possible drug use disorder.

7. Clinician Administered PTSD Scale (CAPS) (Blake et al., 1995). CAPS will determine lifetime and current PTSD. The CAPS measures frequency and intensity of PTSD-related symptoms. Possible scores range from 0 to 136. In a recent review of studies utilizing the CAPS, (Weathers et al., 2001) propose the following severity score ranges for interpreting the CAPS, which are as follows: 0-19 = Asymptomatic/few symptoms; 20-39 = Mild PTSD/subthreshold; 40-59 = Moderate PTSD/threshold; 60-79 = Severe PTSD symptomatology; > 80 = Extreme PTSD. Using these recommendations, in the proposed study, PTSD positive subjects will be positive for lifetime PTSD, related to any lifetime traumatic experience, and will meet CAPS criteria for current, chronic PTSD if they have a current CAPS score of > 40; PTSD negative subjects will be those with a current CAPS score of < 20.

8. Trauma History Questionnaire (THQ) (Green, 1996). This is a 24-item self report inventory which has been modified to provide data on childhood trauma such as sexual or

physical assault. This scale will be used to determine the presence or absence of childhood sexual or physical abuse prior to age 13 and to better characterize the trauma histories of our participants. Responses to items 18-23 focus specifically on the age of occurrence of sexual and physical assault. The Trauma History Questionnaire has been shown to have good test-retest stability (Green, 1996).

9. Life Stressor Checklist-Revised (LSC-R) (Wolfe & Kimerling, 1997). This is a 30-item structured clinical interview for lifetime exposure to stressful life events. The scale emphasizes a number of different potentially traumatic events and assesses the participant's emotional reaction to the stressors and the time period in which the stressors occurred. The LSC-R is reported to have sound psychometric qualities within various PTSD populations (Wolfe & Kimerling, 1997). This measure along with the Trauma History Questionnaire will be used to assess the trauma histories of our participants.

10. PTSD Checklist (PCL) (Blanchard et al., 1996). This is a 17 item self report. Its limitation is that it is keyed to a single traumatic event; e.g., the patient's worst experience in the military. Nonetheless, it has adequate reliability and has been shown to correlate well with scores from the CAPS. It will be used for follow-up of symptoms to assess change with treatment.

11. Pure Tone Audiometry. Section Removed

12. Hamilton Rating Scale for Depression (HRSD). This measure is the primary outcome measure and is completed after each block of 5 sessions throughout the study. The HRSD is the "gold standard" of randomized clinical trials for depression, and the primary measure of most rTMS studies to date. This study will utilize the 24-item version of this instrument (HRSD24) to evaluate depressed mood, vegetative and cognitive symptoms of depression, and comorbid anxiety symptoms. It provides ratings on current DSM-IV symptoms of depression, with the exceptions of hypersomnia, increased appetite, and concentration/indecision.

The Planning Committee, in making this recommendation, examined the outcome measures used in current NIH and industry trials as well as the ACNP criteria for "remission" (Rush et al., 2006). The ACNP recommends that outcome measures reflect all major criteria used in the diagnosis of MDD. Neither the HRSD or the MADRS include all criteria however, they are

widely used in clinical trials and the ACNP report notes that the field has not followed this recommendation and that if one were to use these measures for reasons of comparability (as this Planning Committee recommends), the ACNP report suggests the use of other metrics to assure that remission is complete. For that reason, the Planning Committee recommended additional use of the Quick Inventory of Depressive Symptomatology (QIDS-C16), which meets the ACNP criteria.

Certification of Ratings of HRSD: We plan to follow the NIH protocol procedures for administration and certification of the HRSD ratings. This will include the use of a prepared script to help administer the HRSD. Certification of all raters at a participating site will be verified prior to enrollment. This will be done by shipping recordings of mock interviews (non-patient) to the sites where trained raters have determined a “gold standard HRSD score”. Site raters will then submit their scores. Following NIH procedures, large deviations will be noted, and a rater can have an additional test. This can be repeated for a total of 3 times until the site is told they must find another rater.

Longitudinal Quality Control for HRSD: Following NIH procedures, to ensure that HRSD do not “drift” over time, one HRSD recording will be circulated to evaluators at all participating sites every 6 months. The evaluators will be asked to rate this recording and to return their ratings. Evaluators who drift greater than 3 points on the HRSD total score will receive telephone consultation followed by one additional HRSD recording.

13. Montgomery Asberg Depression Rating Scale (MADRS). As another measure of depression, the Montgomery-Asberg Depression Rating Scale (MADRS) has been used with increasing frequency in recent years to measure outcome in antidepressant efficacy trials. It offers an alternative view of depressive illness, and may be sensitive to depressive symptoms that are not easily captured in the context of the HRSD, such as hypersomnia, increased appetite, and concentration/indecision.

14. Beck Depression Inventory (BDI). This measure is a 21-item self-report test presented in a multiple choice format which measures presence and extent of depression. Each of the 21 items addresses a specific symptom or attitude that pertains to depressed patients, and which are consistent with descriptions of the depression within the peer-reviewed literature. While generally deemed less reliable than scales score by a trained rater (for example, the HRSD),

the Beck scale is easy to administer, and provides convenient means by which patients can effectively communicate their own perception of their mood state.

15. Quick Inventory of Depressive Symptomatology (QIDS-C16). The ACNP recommends that outcome measures reflect all major criteria used in the diagnosis of MDD. For that reason the Planning Committee recommended additional use of the Quick Inventory of Depressive Symptomatology (QIDS-C16), which meets the ACNP criteria (Rush et al., 2003). The HRSD does not measure hypersomnia, weight gain or problems with concentration or decision making.

16. Columbia – Suicide Severity Rating Scale (C-SSRS). Suicide is a rare event. As such, suicide rates cannot be used as an outcome measure for an rTMS study. Similarly, the study is of too short a duration to expect to find a significant difference in numbers or lethality of suicide attempts between treatment and placebo (sham rTMS) groups. Nonetheless, there are two areas that can be expected to change with successful rTMS treatment: preoccupation with suicidal ideations or plans. Because this study uses both a lead in period prior to treatment and a sham rTMS treatment group, we will be able to compare the rate of parasuicidal behavior in these patients, who are at more serious risk of a suicide completion. One of the newer methods of monitoring patients at risk for suicide is the C-SSRS. The C-SSRS assesses suicidal ideation as well suicidal behavior over a specified time period and is frequently employed by the Food and Drug Administration in research to determine if suicidality is an adverse effect. The form will be collected at multiple timepoints in during the course of the study. Initially, it will be collected at baseline to serve as a screener for persons reporting suicidal ideation or behaviors in the past six months. It will also be completed weekly during acute treatment and then monthly during the follow-up phase to monitor for the presence of suicidal ideation or behaviors. The sensitivity of this instrument will allow us to identify even “minor” suicide “gestures” as well as more serious attempts.

17. Beck Hopelessness Scale (BHS) (Beck et al., 1974). The Beck Hopelessness Scale is a self-report measure consisting of 20 “yes/no” items. A total severity of hopelessness is calculated from summing the 20 items and guidelines for interpretation for scores are as follows: 0-3 = minimal hopelessness; 4-8 = mild hopelessness; 9-14 = moderate hopelessness; and 15-20 = severe hopelessness. The BHS will be given at screening, weekly during acute treatment and taper phases and then monthly during the follow-up phase.

18. Beck Scale for Suicide Ideation (BSS). To help clinicians screen psychiatric patients for suicidal ideation, the Beck Scale for Suicide Ideation (Beck and Steer, 1991) was developed, and is herein referred to as the BSS. This self-report measure consists of 21 items and is one of the most thorough assessments of both active and passive suicidal ideation. Respondents are asked to rate the severity of each item on a 3-point scale with scores ranging from 0 to 2. The first five items on the BSS are regarded as a screener for suicidal ideation and assess one's desire to live, desire to die, reasons to live and reasons to die, and suicidal ideation. The remainder of the BSS assesses the duration and frequency of suicidal ideation, ambivalence regarding suicidal ideation, reasons for living / deterrents for suicide, suicide plan / opportunity to enact plan, expectations for following through after an attempt, preparations that have been made to ready for a suicide, past suicide attempts, and wish to die during past suicide attempts. It should be noted that the psychiatrist responsible for the assessment of the patient is responsible for performing a more detailed assessment of any patient showing an increase in BSS score. The BSS will be given at screening, weekly during acute treatment and taper phases and then monthly during the follow-up phase.

Suicidal ideation, hopelessness, agitation, aggression, and depressive symptoms can also be derived from the HRSD and the MADRS, which is also being rated on each patient. The advantages of the HRSD and the MADRS are that they are interviewer-scored scales that focus not only on ideation, but also on psychotic symptoms, and somatic symptoms. Thus, this study, in contrast to the other multisite trials of rTMS, will not only be different because of the population (veterans with TRMD) that it treats, but also because it incorporates five scales that enable evaluation of both ideation and intent (CSSRS and BSS), hopelessness (BHS), and mood, psychotic, and somatic symptoms (HRSD, MADRS).

19. Health Services: Veterans RAND 36 Item Health Survey (VR-36). The VR-36 (formerly known as the SF-36V) is a self-administered survey that measures eight dimensions of health: physical functioning, role limitations due to physical health, bodily pain, general health perceptions, vitality, social functioning, role limitations due to emotional problems, and mental health. It yields scale scores for each of these eight health domains, and two summary measures of physical and mental health: the Physical Component Summary (PCS) and Mental Component Summary (MCS). The VR-36 includes two additional items that assess how much physical and emotional health have changed over the previous year. The VR-36 is a generic measure, as opposed to one that targets a specific age, disease, or treatment group. Thus, it

CSP #556 "The Effectiveness of rTMS in Depressed VA Patients"

Version 4.6, February 2016

Main Section of Protocol

has been useful in assessing the health of general and specific populations, comparing the relative burden of diseases, differentiating the health benefits produced by a wide range of treatments, and screening individual patients. The applicability of the VR-36 is apparent from its widespread use.

20. State-Trait Anger Expression Inventory -2 (STAXI-2). The STAXI-2 is a 57-item self-report measure of the experience, expression, and control of anger. The measure consists of six scale, five subscales, and Anger Expression Index which provides a measure of total anger expression. The STAXI-2 is frequently included in risk assessments for violence and will be used as such in the current protocol.

21. Blessed Orientation Memory Concentration Test (BOMC). The BOMC (Katzman, Brown, Fuld, Peck, Schechter, & Schimmel, 1983) is a 6-item screening measure of cognitive impairment which takes approximately 5 minutes to administer. The measure consists of 3 orientation questions, listing months backwards, a name and address memory phrase, and counting backwards from 20 to 1. This measure is fairly sensitive to milder levels of cognitive impairment.

22. Neuropsychological Battery. We propose to use a battery that is sensitive to the potential cognitive effects of rTMS. rTMS may improve cognitive function as depression is lifted, or it could have the potential for impairing function. A battery has been designed to be sensitive to such potential effects and has been used in previous studies of the effectiveness of rTMS. We propose to use measures that have been used in previous studies of rTMS as they have proven to be sensitive and it will also provide a basis for comparison of the VA patients entering this study with patients who have participated in other studies of rTMS.

The cognitive assessments will be administered at screening, at the end of the acute treatment phase and at the end of the 24 week follow-up phase. These measures are widely used in the literature and have been shown to be effective when working with severely depressed patients

Testing will include measures of Executive Function, Attention, Memory, Visuospatial Ability, Processing Speed, Psychomotor Function, and premorbid intelligence.

Executive functioning will be assessed using the **Controlled Oral Word Association (COWA) Test**, which is a test of verbal fluency. Participants are asked to produce as many words that

begin with a specific letter (F, A, or S) as they can within one minute. The participant is then asked to name as many animal names as possible within one minute (Spreen and Strauss, 2006).

Attention will be assessed using the **Stroop Color and Word test** (Golden, 1978). This measure consists of three pages: a Word page with 100 color words printed in black ink; a Color page with 100 X's printed in colored ink; and a Color-Word page that contains words from the Word page printed in colors (the word and the color do not match). Participants are asked to read as many words or name as many colors as possible in 45 seconds.

